#### **5.3.4.3 Dose Modifications for Liver Function Test Abnormalities**

Doses of nivolumab should be delayed for the following LFT abnormalities:

- If a patient has a baseline AST/ALT that is within the normal limits, delay dosing for nivolumab-related Grade 2 (>3 to 5 x ULN) elevations
  - Nivolumab may be resumed if the value improves to Grade 1 ( $\leq 3$  x ULN) or better

- If a patient has a baseline AST/ALT in the Grade 1 range (ULN to  $\leq 3 \times$  ULN), delay dosing for nivolumab-related Grade 3 ( $>5$  to  $8 \times$  ULN) elevations
  - Nivolumab may be resumed if the value improves to Grade 2 ( $>3$  to  $5 \times$  ULN) or better
- If a patient has a baseline total bilirubin that is within normal limits, delay dosing for nivolumab-related Grade 2 elevations ( $>1.5$  to  $3 \times$  ULN)
  - Nivolumab may be resumed if the bilirubin improves to Grade 1 or better ( $\leq 1.5 \times$  ULN)
- If a patient has a baseline Grade 1 elevation of total bilirubin (ULN to  $\leq 1.5 \times$  ULN), delay dosing for nivolumab-related Grade 3 elevations in the range of  $>3$  to  $5 \times$  ULN
  - Nivolumab may be resumed if the total bilirubin improves to Grade 2 or better ( $\leq 3 \times$  ULN)

Doses of nivolumab should be discontinued permanently for the following LFT abnormalities:

- AST or ALT  $>8 \times$  ULN or drug-induced liver injury (DILI)
- Total bilirubin  $>5 \times$  ULN or DILI
- Concurrent AST or ALT  $>3 \times$  ULN and total bilirubin  $>2 \times$  ULN

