##### **5.3.4.1 Dose Delays**

Dose delays for nivolumab-related liver function test (LFT) abnormalities are described in Section 5.3.4.3. Otherwise, nivolumab administration should be delayed for the following:

- Any  $\geq$  Grade 2 non-skin, nivolumab-related AE, with the following exception:
  - Grade 2 nivolumab-related fatigue or laboratory abnormalities, other than LFT abnormalities (see Section 5.3.4.3), do not require a treatment delay
- Any Grade 3 skin, nivolumab-related AE
- Any Grade 3 nivolumab-related laboratory abnormality, other than LFT abnormalities (see Section 5.3.4.3), with the following exceptions for lymphopenia or asymptomatic amylase or lipase:
  - Grade 3 lymphopenia does not require dose delay
  - Any  $\geq$  Grade 3 nivolumab-related amylase or lipase abnormality that has been evaluated clinically and radiographically and is without evidence of pancreatitis does not require dose delay. The medical monitor should be consulted for such  $\geq$  Grade 3 amylase or lipase abnormalities
- Any AE, laboratory abnormality, or intercurrent illness which, in the judgment of the investigator, warrants delaying the dose of nivolumab

Patients who require delay of nivolumab should be re-evaluated weekly or more frequently if clinically indicated. Nivolumab may be resumed at the next scheduled treatment cycle if the AE recovers to  $\leq$  Grade 1 or baseline, with the following exceptions:

- Patients may resume nivolumab treatment in the presence of Grade 2 fatigue
- Patients who have not experienced a Grade 3 nivolumab-related skin AE may resume nivolumab treatment in the presence of Grade 2 skin toxicity
- Nivolumab-related pulmonary toxicity, diarrhea, or colitis must have resolved to baseline before nivolumab treatment is resumed. Patients with persistent Grade 1 pneumonitis after completion of a steroid taper over at least 1 month may be eligible for continued nivolumab treatment if discussed with and approved by the medical monitor
- Nivolumab-related endocrinopathies adequately controlled with only physiologic hormone replacement may resume nivolumab treatment after consultation with the medical monitor

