#### **5.3.4.2 Dose Discontinuation**

Dose discontinuations for LFT abnormalities are described in Section 5.3.4.3. Otherwise, nivolumab treatment should be permanently discontinued for the following:

- Any Grade 2 nivolumab-related uveitis, eye pain, or blurred vision that does not respond to topical therapy and does not improve to Grade 1 severity within 6 weeks or requires systemic treatment
- Any Grade 3 non-skin, nivolumab-related AE lasting more than 7 days, with the following exceptions for laboratory abnormalities other than LFT abnormalities (see Section 5.3.4.3), nivolumab-related uveitis, pneumonitis, bronchospasm, hypersensitivity reactions, infusion reactions, and endocrinopathies:
  - Grade 3 nivolumab-related uveitis, pneumonitis, bronchospasm, hypersensitivity reaction, or infusion reaction of any duration requires discontinuation
  - Grade 3 nivolumab-related endocrinopathies adequately controlled with only physiologic hormone replacement do not require discontinuation
  - Grade 3 nivolumab-related thrombocytopenia lasting more than 7 days or associated with bleeding; other Grade 3 nivolumab-related laboratory abnormalities other than LFT abnormalities (see Section 5.3.4.3), do not require treatment discontinuation
- Any Grade 4 nivolumab-related AE or laboratory abnormality other than LFT abnormalities (see Section 5.3.4.3), except for the following events:
  - Grade 4 neutropenia  $\leq$  7 days
  - Grade 4 lymphopenia or leukopenia

- Isolated Grade 4 amylase or lipase abnormalities not associated with symptoms or clinical manifestations of pancreatitis; consult the medical monitor for Grade 4 amylase or lipase abnormalities
- Isolated Grade 4 electrolyte imbalances/abnormalities not associated with clinical sequelae and are corrected with supplementation/appropriate management within 72 hours of their onset
- Grade 4 nivolumab-related endocrinopathy AEs, such as adrenal insufficiency, adrenocorticotrophic hormone deficiency, hyper- or hypothyroidism, or glucose intolerance, which resolve or are adequately controlled with physiologic hormone replacement (corticosteroids, thyroid hormones) or glucose-controlling agents, respectively, may not require discontinuation after discussion with the medical monitor
- Any AE, laboratory abnormality, or intercurrent illness which, in the judgment of the Investigator, presents a substantial clinical risk to the patient with continued nivolumab dosing

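### For patients with normal baseline liver tests, Section 5.3.4.3 holds nivolumab for a moderate rise but states no hold for a larger rise below the stopping limit

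*Protocol*

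**What the plan says.** Section 5.3.4.3 of the protocol gives four delay rules, split by analyte and baseline.

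- AST/ALT, normal baseline: "delay dosing for nivolumab-related Grade 2 (>3 to 5 x ULN) elevations".
- AST/ALT, Grade 1 baseline: delay at Grade 3, given as >5 to 8 × ULN.
- Bilirubin, normal baseline: "If a patient has a baseline total bilirubin that is within normal limits, delay dosing for nivolumab-related Grade 2 elevations", given as >1.5 to 3 × ULN.
- Bilirubin, Grade 1 baseline: "delay dosing for nivolumab-related Grade 3 elevations in the range of" >3 to 5 × ULN.

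The stopping rules follow: "Doses of nivolumab should be discontinued permanently for the following LFT abnormalities". They are AST or ALT >8 × ULN, total bilirubin >5 × ULN, drug-induced liver injury (DILI), or AST/ALT >3 × ULN together with bilirubin >2 × ULN. They apply at any baseline.

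The neighbouring sections send the reader here. Section 5.3.4.1 opens with "Dose delays for nivolumab-related liver function test (LFT) abnormalities are described in Section 5.3.4.3" and Section 5.3.4.2 with "Dose discontinuations for LFT abnormalities are described in Section 5.3.4.3". Each then introduces its own list with the word *otherwise*. Section 5.5.2 also points to 5.3.4.3 for dose modifications. Section 6.1 requires chemistry results, apart from gamma-glutamyl transpeptidase and thyroid tests, to be reviewed before dosing.

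**The concern.** A dose-hold rule should not become weaker as the abnormality grows. Here the normal-baseline bands have upper ends, and the stopping limits do not begin where the bands finish. Read literally, the section requires a hold at AST 4 × ULN and gives no instruction at AST 6 × ULN, while the same value of 6 from a Grade 1 baseline does require a hold.

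That reverses the ordering in Section 5.6.3, under which a patient starting at Grade 1 is managed one grade more leniently than a patient starting from normal. It suggests that the words *or higher* were left out, not that a lighter rule was intended.

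The stake is consistency of patient safety management. Sites looking up the same pre-dose result in the section meant to standardise the response could act differently.

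**Working it through.** The plan gives no figure to reproduce. The check is a comparison of the printed ranges, all from Section 5.3.4.3. It takes an isolated value without DILI and without the concurrent AST/ALT and bilirubin criterion. Scanning each analyte from 0 to 10 × ULN in steps of 0.01 gives:

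| Analyte and baseline | Explicit delay (× ULN) | No explicit action above the delay band | Permanent stop |
|---|---|---|---|
| AST/ALT, normal | >3 to 5 | >5 to 8 | >8 |
| AST/ALT, Grade 1 | >5 to 8 | none | >8 |
| Bilirubin, normal | >1.5 to 3 | >3 to 5 | >5 |
| Bilirubin, Grade 1 | >3 to 5 | none | >5 |

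**Width of the gap, normal baseline**

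- AST/ALT, from first delay threshold to stopping limit: 8 − 3 = 5 units. Covered: 5 − 3 = 2, and 2/5 = 40%. Uncovered: 8 − 5 = 3, and 3/5 = 60%.
- Bilirubin: 5 − 1.5 = 3.5 units. Covered: 3 − 1.5 = 1.5, and 1.5/3.5 = 43%. Uncovered: 5 − 3 = 2, and 2/3.5 = 57%.

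**Which patients fall in the gap, with both analytes normal at baseline**

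- AST/ALT gap: neither transaminase may lie in >3 to 5, since that triggers the printed delay. Bilirubin must be ≤1.5 × ULN, because >1.5 to 2 triggers the bilirubin delay and >2 triggers the concurrent stop.
- Bilirubin gap: AST and ALT must both be ≤3 × ULN, because anything higher triggers the concurrent stop.
- It must be the first such value. A patient already on hold cannot resume until AST/ALT is ≤3 or bilirubin ≤1.5 × ULN.

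**Can the missing band be read in from the grade label?** Not safely. The normal-baseline rule names Grade 2 with a stated upper limit, and the Amendment 1 rationale in Appendix F says that the protocol's liver ranges do not match CTCAE grades exactly.

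**After the change proposed below**, the delay covers >3 to 8 (5/5 units) and >1.5 to 5 (3.5/3.5 units), meeting the stopping limits with nothing between.

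**The case against.** The strongest reply is that other text covers these values.

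- *General delay rule.* Section 5.3.4.1 delays nivolumab for any related non-skin adverse event of Grade 2 or above, and its exception is confined to "Grade 2 nivolumab-related fatigue or laboratory abnormalities, other than LFT abnormalities". Section 5.3.4.2 has a similar carve-out in its rule on Grade 3 events lasting more than 7 days. If *otherwise* removed liver tests from these lists altogether, the carve-outs would be redundant. Section 5.3.4.3 itself labels the two bands Grade 3. This is a fair reading, but not the only one: the separate Grade 3 laboratory item in 5.3.4.1 leaves out liver tests and points back to 5.3.4.3.
- *Investigator judgment.* Section 5.3.4.1 also lists "Any AE, laboratory abnormality, or intercurrent illness which, in the judgment of the investigator, warrants delaying the dose of nivolumab", and 5.3.4.2 has a parallel item. These are real safeguards, but discretionary ones, whereas the milder value has a stated rule.
- *Investigator's Brochure.* Sections 5.3.4, 5.5.2 and 5.6.3 refer to its appendices, and 5.6.3 makes a hepatic exception only for Grade 1 baselines, so a normal-baseline patient would follow the unmodified algorithm. That may supply a hold. It cannot be checked here.

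Two further points have force. The case is narrow, and because treatment is at most four cycles, a nivolumab-related value can bear on at most three dosing decisions per patient (doses 2 to 4). The intended action might also be stricter than delay and resume.

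What stands: the consequence is limited, no text permits dosing in the gap, and the fix must not soften a stricter rule. What does not stand is that the printed rule is adequate. None of these sources clearly provides an explicit hold within the documents.

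**Conclusion.** The point holds as a drafting error in a stated safety rule. For normal-baseline patients, Section 5.3.4.3 has no explicit hold for a first isolated AST/ALT of >5 to 8 × ULN or bilirubin of >3 to 5 × ULN, although it has one for smaller rises and for the same values from a Grade 1 baseline.

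The gap is 60% and 57% of the respective ranges between first hold and permanent stop. Those percentages describe the text, not patients or risk; the frequency of such values is unknown.

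The conclusion rests on reading the bands literally, on the value being related to nivolumab, and on there being no DILI. It does not mean that sites have no rule at all or that patients would be dosed. The CR endpoint and its test are unaffected. It should be corrected because the rule concerns hepatic safety and is easy to repair.

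**What to change.** In Section 5.3.4.3, reword the two normal-baseline bullets:

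- AST/ALT: delay for nivolumab-related values >3 × ULN (Grade 2 or higher), up to the existing permanent-discontinuation limits.
- Total bilirubin: delay for nivolumab-related values >1.5 × ULN (Grade 2 or higher), up to the same limits.

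Keep the resumption thresholds (≤3 and ≤1.5 × ULN) and every stopping rule. Add one sentence stating that any stricter discontinuation requirement in Section 5.3.4.2 (including the rule on Grade 3 events lasting more than 7 days, if it applies to liver tests) or in the Investigator's Brochure hepatic algorithm still applies. That sentence is part of the fix: without it, delay-and-resume wording for Grade 3 values could be taken to relax those rules. If the sponsor knows whether the 7-day rule is meant to cover liver tests, the same text can say so outright.

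The cost is two bullets and one sentence, by amendment or clarification letter. No new tests are needed, since AST, ALT and bilirubin are already in the pre-dose chemistry panel. A few doses may be held that a literal reading would have allowed.

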### **5.3.5 Storage and Handling**

Nivolumab should be stored at 2–8°C and protected from light, freezing, and shaking. Care should be taken when handling and preparing nivolumab. Partially used vials should be disposed at the site per the procedures for the disposal of anticancer drugs.

Drug accountability instructions are provided in the Pharmacy Binder.

### **5.3.6 Packaging and Labeling**

Drug product vials may be labeled as nivolumab, the USAN and the INN, or as BMS-936558, the compound code; the 2 names can be used interchangeably.

### **5.3.7 Preparation**

The drug product solution should be visually inspected for particulate matter and discoloration prior to administration. The vial should be discarded if the solution is cloudy, is discolored, or contains extraneous particulate matter other than a few translucent-to-white, proteinaceous particles. The vial should not be shaken.

Detailed drug preparation instructions are provided in the Pharmacy Binder.

## **5.4 Required Premedication and Postmedication**

Routine premedication should not be administered for the prevention of infusion-related reactions prior to the first dose of study drug(s).

#### **5.4.1 Patients in Parts 1 and 2**

Prophylactic premedication for prevention of infusion-related reactions is to be administered prior to combination treatment on Day 1 of each 21-day cycle beginning with Cycle 2.

Hydrocortisone 100 mg IV or equivalent, and an antihistamine (e.g., diphenhydramine 25–50 mg IV or equivalent) should be given at least 30 minutes prior to infusion of brentuximab vedotin. Patients who experience an infusion-related reaction with this premedication regimen should receive premedication with methylprednisolone 40 mg IV (or equivalent) with an antihistamine for all subsequent cycles. Additional premedications for symptom management (e.g., acetaminophen and/or ondansetron) may also be given at the discretion of the investigator.

If treatment with nivolumab or brentuximab vedotin is discontinued, premedications may be reduced or stopped at the discretion of the investigator during single-agent treatment for subsequent cycles.

Patients should be individually evaluated to assess the need for tumor lysis prophylaxis prior to the first dose of brentuximab vedotin. Patients should receive prophylaxis as appropriate per the institutional standards.

#### **5.4.2 Patients in Part 3**

Prophylactic premedication with antihistamines for prevention of infusion-related reactions is to be administered prior to combination treatment on Day 1 of each 21-day cycle beginning with Cycle 1. Antihistamines (e.g., diphenhydramine 50 mg IV or equivalent and famotidine 40 mg IV or equivalent) should be given at least 30 minutes prior to infusion of brentuximab vedotin. Patients who experience an infusion-related reaction with this premedication regimen should receive additional premedication with dexamethasone 0.2 mg/kg (maximum 10 mg IV or equivalent) for all subsequent cycles.

Additional premedications for symptom management (e.g., acetaminophen and/or ondansetron) may also be given at the discretion of the investigator.

If treatment with nivolumab or brentuximab vedotin is discontinued, premedications may be reduced or stopped at the discretion of the investigator during single-agent treatment for subsequent cycles.

Patients should be individually evaluated to assess the need for tumor lysis prophylaxis prior to the first dose of brentuximab vedotin. Patients should receive prophylaxis as appropriate per the institutional standards.

### **5.5 Concomitant Therapy**

All concomitant medications, blood products, and radiotherapy administered will be recorded from Day 1 (predose) through the safety reporting period for brentuximab vedotin or 100 days after the patient's last dose of nivolumab, whichever occurs later. Any concomitant medication given for a study protocol-related AE should be recorded from the time of informed consent.

### **5.5.1 Required Concomitant Therapy**

Patients should be up-to-date on any recommended vaccinations prior to study entry. Additional vaccination(s) during each cycle of study treatment must be approved by the medical monitor.

Required premedications to prevent infusion-related reactions are described in Section [5.4.1](#) and Section [5.4.2](#).

### **5.5.2 Allowed Concomitant Therapy**

The use of platelet and/or RBC supportive growth factors or transfusions when applicable is allowed. The use of colony stimulating factors for the treatment of neutropenia per institutional practice is permitted during therapy.

Patients who are receiving strong CYP3A4 inhibitors concomitantly with brentuximab vedotin should be closely monitored for adverse reactions.

Routine prophylaxis with vaccines is permitted prior to study entry; it is recommended that vaccines used do not contain live micro-organisms.

Patients are permitted the use of topical, ocular, intra-articular, intranasal, and inhalational corticosteroids (with minimal systemic absorption). Stable adrenal replacement steroid doses >10 mg daily prednisone, or prednisone equivalent, are permitted. A brief (less than 3 weeks) course of corticosteroids for prophylaxis (e.g., contrast dye allergy) or for treatment of non-autoimmune conditions (e.g., delayed-type hypersensitivity reaction caused by a contact allergen) is permitted. Treatment with 0.5 to 2 mg/kg/day methylprednisolone IV (or oral equivalent), followed by a taper, is recommended for certain immune-mediated AEs; see Section [5.3.4.3](#) for dose modifications and relevant management algorithms in Appendix 3 of the nivolumab Investigator's Brochure. Treatment with 0.5 to 1 mg/kg corticosteroids, followed by taper, is recommended for Grade 2 or 3 creatinine elevation or nephritis.

Peripheral blood stem cells may be mobilized following Cycle 4 at the discretion of the investigator. However, stem cell collection may occur in prior cycles after discussion with the medical monitor. Collection of peripheral blood stem cells for ASCT, if applicable, should occur per institutional standard of care. If stem cell collection after Cycle 4 is inadequate, additional collection of peripheral blood stem cells for ASCT may be performed per institutional standards, if applicable.

At the discretion of the treating physician, consolidative radiotherapy or consolidative treatment with single-agent brentuximab vedotin may be given post-ASCT.

Allowed medications to manage infusion-related reactions are described in Section [5.6.1.1](#) and Section [5.6.1.2](#).

### **5.5.3 Prohibited Concomitant Therapy**

Patients may not receive other investigational drugs, immunosuppressive medications, radiotherapy, or systemic anti-neoplastic therapy during the study. Exceptions are noted in Section [5.5.2](#).

## **5.6 Management of Adverse Reactions**

### **5.6.1 Management of Infusion Reactions**

Infusion-related reactions may occur during the infusion of study treatment(s). The infusion should be administered at a site properly equipped and staffed to manage anaphylaxis should it occur. All supportive measures consistent with optimal patient care should be given throughout the study according to institutional standards. Supportive measures may include extending the infusion time and/or administering medications for infusion-related reactions.

Infusion or hypersensitivity reactions may occur to either brentuximab vedotin or nivolumab. If such a reaction were to occur, it might manifest with fever, chills, rigors, headache, rash, pruritus, arthralgias, hypotension, hypertension, bronchospasm, or other allergic-like reactions. Infusion reactions should be graded according to NCI CTCAE (Version 4.03) guidelines.

#### **5.6.1.1 Patients in Parts 1 and 2**

Premedication for the prevention of infusion reactions should be administered beginning with Cycle 2, at least 30 minutes prior to dosing study drug(s), and should include an antihistamine and low-dose corticosteroid, as described in Section [5.4.1](#). If the onset of a reaction occurs during an infusion, the infusion may be interrupted for treatment of the infusion-related reaction, including treatment with antihistamines, corticosteroids, bronchodilator therapy, and/or antipyretics, as appropriate. Patients who experience a Grade 3 infusion-related reaction to brentuximab vedotin or nivolumab may potentially receive additional treatment with the study drug(s) at the discretion of the investigator after discussion with the sponsor.

If anaphylaxis or a Grade 4 infusion-related reaction occurs, administration of the implicated agent(s) (brentuximab vedotin and/or nivolumab) should be immediately and permanently discontinued.

In case of late-occurring hypersensitivity symptoms to nivolumab (e.g., appearance of a localized or generalized pruritus within 1 week after nivolumab treatment), symptomatic treatment may be given (e.g., oral antihistamine or corticosteroids).

#### **5.6.1.2 Patients in Part 3**

For patients in Part 3, prophylactic premedication with antihistamines for prevention of infusion-related reactions is to be administered prior to combination treatment on Day 1 of each 21-day cycle as described in Section [5.4.2](#). Patients who experience an infusion-related reaction with this premedication regimen should receive additional premedication with dexamethasone 0.2 mg/kg (maximum 10 mg IV or equivalent) as well as the antihistamines

as described in Section 5.4.2 for all subsequent cycles. Additional premedication for symptom management (e.g., acetaminophen and/or ondansetron) may also be given at the discretion of the investigator. If the onset of a reaction occurs during an infusion, the infusion may be interrupted for treatment of the infusion-related reaction, including treatment with antihistamines, corticosteroids, and/or bronchodilator therapy, as appropriate. Patients who experience a Grade 3 infusion-related reaction to brentuximab vedotin or nivolumab may potentially receive additional treatment with the study drug(s) at the discretion of the investigator after discussion with the sponsor.

If anaphylaxis or a Grade 4 infusion-related reaction occurs, administration of the implicated agent(s) (brentuximab vedotin and/or nivolumab) should be immediately and permanently discontinued.

In case of late-occurring hypersensitivity symptoms to nivolumab (e.g., appearance of a localized or generalized pruritus within 1 week after nivolumab treatment), symptomatic treatment may be given (e.g., oral antihistamine or corticosteroids).

